Blood samples will be collected from each NHV (Cohorts 1-5) participant during the study for Complement analysis after dose 1 (all cohorts). Two blood samples will be collected at each collection time. One sample will be processed to produce serum for complement CH50 analysis, and one sample will be processed to produce plasma, which will be analyzed to determine the level of split products Bb, C5a, C4a, and C3a. Initially the 0 (pre-) and 2-hour post-dose samples will be analyzed, with the remaining samples analyzed only if a change from pre-dose baseline is observed at 2 hours.

Excretion and Metabolism:

Seven blood samples will be collected from each subject for metabolic analysis after dose 1 (Cohorts 2-5) per the Schedule of Assessments. Samples will be frozen at -80°C for analysis outside of this study.

Urine collections will be performed after dosing per the Schedule of Assessments.

Data Analysis:

Two separate data analyses will be performed, one for all subjects through EOS (Day 29 for NHVs and Day 113 for CHB patients), and one additional and separate analysis for CHB patients who consent to the additional follow up through Day 337 (Cohort 12 only) or Day 393. Separate analyses including and excluding Cohort 12 may also be completed.

Screening, Compliance, Tolerability and Safety Data:

In general, safety analyses will be performed and the results summarized by cohort. Post-treatment safety assessments will be compared with measurements recorded at baseline. Treatment emergent AEs will be summarized using the latest version of the Medical Dictionary for Regulatory Activities (MedDRA) by System Organ Class (SOC) and Preferred Term (PT). The incidence and frequency of AEs, SAEs, related AEs, related SAEs, and AEs leading to discontinuation, will be summarized by cohort per SOC, PT, and severity. All Adverse Events will also be presented in listings. The duration of AEs will be determined and included in listings, along with the action taken and outcome. The incidence of laboratory abnormalities will be assessed using descriptive summary statistics and shift tables. Vital sign measurements will be summarized at each scheduled time point using descriptive statistics. Abnormal physical examination findings will be summarized by time point and presented in subject listings. ECG parameters, changes from baseline, and qualitative assessments will be summarized. Pregnancy and FSH test results will be listed separately by time point.

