CHB cohorts 1b, 1c, 2b, 3b, 4b and 5b will each enroll a minimum of 4 and a maximum of 8 subjects and the remaining CHB cohorts (except Cohort 12) will each recruit a maximum of 4 chronic hepatitis B patients, with all subjects receiving three doses of ARO-HBV at dose intervals ranging from once every week to once every 4 weeks in an open label fashion. All CHB cohorts except Cohorts 8 and 9 will include CHB patients regardless of NUC or HBeAg status. Cohort 8 will include HBeAg(+) and treatment naïve patients, and Cohort 9 will include HBeAg(+) and entecavir or tenofovir experienced patients. CHB patients on current nucleos(t)ide (NUC) therapy (entecavir or tenofovir) will stay on NUC therapy for the study duration. CHB patients not on NUC therapy (NUC naïve) will be started on either entecavir or tenofovir (selection between entecavir and tenofovir based on site Principal Investigator (PI) discretion) on Day 1. Cohort 12 will enroll 12 CHB patients who will either enter the study on NUCs or start NUCs on Day 1. Cohort 12 patients will also initiate daily JNJ-56136379 (JNJ-6379) 250 mg on Day 1 and continue through Day 84.

CHB cohorts will be multi-dosed as follows:

- Cohort 1b: 25 mg ARO-HBV, at Days 1, 29 and 57
- Cohort 1c: 50 mg ARO-HBV, at Days 1, 29 and 57
- Cohort 2b: 100 mg ARO-HBV, at Days 1, 29 and 57

- Cohort 3b: 200 mg ARO-HBV, at Days 1, 29 and 57
- Cohort 4b: 300 mg ARO-HBV, at Days 1, 29 and 57
- Cohort 5b: 400 mg ARO-HBV, at Days 1, 29 and 57
- Cohort 6: 100 mg ARO-HBV, at Days 1, 15 and 29
- Cohort 7: 100 mg ARO-HBV, at Days 1, 8 and 15
- Cohort 8 (HBeAg +, Treatment naïve): 300 mg ARO-HBV, at Days 1, 29 and 57
- Cohort 9 (HBeAg +, NUC (entecavir/tenofovir) experienced): 300 mg ARO-HBV, at Days 1, 29 and 57
- Cohort 10: 200 mg ARO-HBV, at Days 1, 8 and 15
- Cohort 11: 300 mg ARO-HBV, at Days 1, 8 and 15
- Cohort 12: 200 mg ARO-HBV, at Days 1, 29 and 57 + 250 mg daily JNJ-6379 + NUCs

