### CHB Cohorts

All CHB patients in each of the 13 CHB cohorts will receive ARO-HBV (alone or in combination with JNJ-6379) and daily NUC, and no randomization is applied.

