### 3. STATISTICAL CONSIDERATIONS

Data will be handled and processed according to the sponsor's representative (Novotech (Australia) Pty Ltd) Standard Operating Procedures (SOPs), which are written based on the principles of GCP.

All data collected on the eCRFs will be presented in the data listings and will be listed and sorted by subject number and visit, where applicable. All summaries will present the data by ARO-HBV dose level/cohort and overall (total subjects), as applicable.

Data collected during the main study (up to the Day 29 or Day 113 EOS visits) and at the additional follow-up visits (CHB cohorts only) will be presented in the same summary table, as appropriate. The first part of each table will present the main study results for the specific analysis. The second part of each table will include all data collected during the study, including data collected during the follow-up period, for the subset of CHB patients that consented to participate in the follow-up. All data will be included in the listings, and data collected during the follow-up period will be flagged in all event/medication-based listings. Separate figures that include all data will be presented for the subset of patients that participated in the follow-up period.

Unless otherwise stated, the following statistical approaches will be taken:

- Continuous variables: Descriptive statistics will include the number of non-missing values (N), mean, standard deviation (SD), median, minimum, maximum.
- Categorical variables: Descriptive statistics will include frequency counts and percentages per category. Percentages will be rounded to one decimal place, with the denominator being the number of subjects in the relevant population with non-missing data, unless otherwise specified.
- Imputation: No missing data will be imputed generally.
- Confidence intervals (CIs): CIs will be two-sided and will use 95% confidence levels unless specified otherwise.
- Baseline: Baseline values will be defined as the last non-missing observation (pre-dose value closest to the first dose) for each subject prior to the dosing of study medication (i.e. start of injection on Day 1).
- Repeat assessments (Safety): If there is a repeat test, the repeat result will be used in the analysis table and the original result will only be listed in the data listing.

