- Repeat assessments (Virology): Certain virologic assessments such as qHBsAg may be batch analyzed per patient at the end of study. In cases where both batch-analyzed and non-batch analyzed data are available, batch analyzed data will be used in the analysis table and all other results will be listed. In other instances, repeat tests may have been performed for other reasons than batch-analysis. If there is a repeat test, the repeat result will be used in the analysis table and the original result will only be listed in the data listing.

Continuous safety variables will be reported to the same precision as the source data. Derived variables will be reported using the same precision to the value(s) from which they were derived. For the reporting of descriptive statistics, the mean (95% CI) and median will be reported to 1 decimal place more than the source data; the minimum, and the maximum values will be presented to the same precision as the source data; and standard deviation will be

reported to 2 decimal places more than the source data. Rounding is not allowed in the middle of the calculation. It only takes place at the last step to report the final result. Post-dose time points/visits will be calculated relative to start time of injection on Day 1. Study day will be defined as assessment date minus dosing day +1.

The NHV cohorts (Cohorts 1, 2, 3, 4, and 5) will be summarized separately from the CHB cohorts (Cohorts 1b, 1c, 2b, 3b, 4b, 5b, 6, 7, 8, 9, 10,11 and 12). The dose levels (cohorts) will be referred to in the text, tables and listings as follows.

NHV Cohorts:

- Coh1: ARO-HBV (35 mg)
- Coh2: ARO-HBV (100 mg)
- Coh3: ARO-HBV (200 mg)
- Coh4: ARO-HBV (300 mg)
- Coh5: ARO-HBV (400 mg)
- Combined ARO-HBV
- Combined Placebo
- Total (including all ARO-HBV and Placebo)

CHB Cohorts:

- Coh1b: ARO-HBV (25 mg, Q28D)
- Coh1c: ARO-HBV (50 mg, Q28D)
- Coh2b: ARO-HBV (100 mg, Q28D)
- Coh3b: ARO-HBV (200 mg, Q28D)
- Coh4b: ARO-HBV (300 mg, Q28D)
- Coh5b: ARO-HBV (400 mg, Q28D)
- Coh6: ARO-HBV (100 mg, Q14D)
- Coh7: ARO-HBV (100 mg, Q7D)
- Coh8: ARO-HBV (300 mg, Q28D, HBeAg+/Trt Naive)
- Coh9: ARO-HBV (300 mg, Q28D, HBeAg+/NUC)
- Coh10: ARO-HBV (200 mg, Q7D)
- Coh11: ARO-HBV (300 mg, Q7D)
- Coh12: ARO-HBV (200 mg, Q28D) + JNJ-6379 250mg
- Combined ARO-HBV
- Pooled ARO-HBV (300 mg, Q28D)

where Q7D: dosing once every 7 days,  
Q14D: dosing once every 14 days,  
Q28D: dosing once every 28 days

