Summary tables and listings will be produced separately for NHV cohorts (Cohorts 1, 2, 3, 4 and 5) and CHB cohorts (Cohorts 1b, 1c, 2b, 3b, 4b, 5b, 6, 7, 8, 9, 10,11 and 12). The Pooled ARO-HBV (300 mg, Q28D) group will only be presented for the safety outputs.

Due to the large number of treatment columns that will be displayed in the outputs, the results for a specific parameter/visit could span multiple pages. Summaries will be presented by groups of treatments, i.e., if only CHB Coh1b to Coh7 can be fit onto a page, all of the results for these cohorts will be presented on the subsequent pages before the results for the initial visits of the next group of cohorts are presented. Where appropriate, the outputs may also be

transposed to present the treatment information in rows instead of columns to facilitate the review process.

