### **10.1 Adverse Events**

Adverse events (AEs) will be coded using the Medical Dictionary for Regulatory Activities (MedDRA®, the latest available version), and data will be summarized by System Organ Class (SOC) and Preferred Term (PT). The number and percent of subjects reporting each AE will be summarized for each dose level (cohort) and overall. A subject with two or more AEs within the same level of summarization (i.e., SOC or PT) will be counted only once in that level. Percentages will be based on the number of subjects in the Safety Population within each dose level (cohort). The number of AEs reported will also be presented.

Treatment-emergent AEs (TEAEs) are defined as pre-treatment existing conditions that worsen after study drug administration, or events that occur during the course of the study during or after administration of study drug. Only TEAEs will be included in the AE summary tables which will present data by dose level (NHV/CHB cohorts) for active treatment versus pooled placebo subjects (NHV cohorts). In the case of a missing AE start date or stop date, the most conservative approach will be followed to classify AE into TEAE unless it is not possible that the AE could be treatment emergent. AEs that occurred during the follow-up period will only be included in the follow-up table.

A table providing an overall summary of AEs will be produced which will include the number of TEAEs; the number and % of subjects reporting at least one: TEAE, serious TEAE, grade 3 (severe) or higher TEAE, TEAE related to study treatment (related to ARO-HBV or JNJ-6379 [Cohort 12 only]: possibly/probably), serious TEAE related to study treatment, grade 3 or higher TEAE related to the study drug, TEAEs by severity and TEAEs by relationship, drug or study discontinuations due to TEAEs. The table will also be repeated for related (ARO-HBV or placebo) TEAEs.

Additional AE tables will be generated as follows:

- TEAEs by SOC and PT
- TEAEs by decreasing incidence of the PTs in the Combined ARO-HBV group
- Study Drug (ARO-HBV or placebo) Related TEAEs by SOC and PT
- Study Drug (ARO-HBV or placebo) Related TEAEs by decreasing incidence of the PTs in the Combined ARO-HBV group
- Study Drug (JNJ-6379) Related TEAEs by SOC and PT (Cohort 12 only)

- Study Drug (JNJ-6379) Related TEAEs by decreasing incidence of the PTs in the Combined ARO-HBV group (Cohort 12 only)
- TEAEs by Severity
- TEAEs by Relationship to Study Drug (ARO-HBV)
- Treatment Emergent SAEs

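### The CHB Combined ARO-HBV column is undefined and by implication includes Cohort 12, so pooled safety summaries would carry JNJ-6379 effects under an ARO-HBV label

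*SAP*

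**What the plan says.** SAP Section 3 lists the columns for the CHB outputs. The individual cohorts end with "Coh12: ARO-HBV (200 mg, Q28D) + JNJ-6379 250mg". Two pooled columns follow: *Combined ARO-HBV*, with no statement of membership, and "Pooled ARO-HBV (300 mg, Q28D"), whose label fixes its content. Of the second, Section 3 adds: "The Pooled ARO-HBV (300 mg, Q28D) group will only be presented for the safety outputs". No such limit is placed on the first.

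Section 3 also sets a general rule: "All summaries will present the data by ARO-HBV dose level/cohort and overall (total subjects), as applicable". The healthy-volunteer column list has a separate Total line; the CHB list has none. SAP 2.5 describes the patients this way: "All CHB patients in each of the 13 CHB cohorts will receive ARO-HBV (alone or in combination with JNJ-6379) and daily NUC". SAP 2.1 gives the difference in regimen: "Cohort 12 patients will also initiate daily JNJ-56136379 (JNJ-6379) 250 mg on Day 1 and continue through Day 84".

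In SAP 10.1, the table of JNJ-6379-related events by frequency is ordered "by decreasing incidence of the PTs in the Combined ARO-HBV group (Cohort 12 only"). In the overall adverse event summary, the treatment-related row counts relatedness to ARO-HBV or, in Cohort 12, to JNJ-6379.

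The protocol synopsis (Data Analysis) says: "Separate analyses including and excluding Cohort 12 may also be completed". The SAP specifies no combined column without Cohort 12.

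**The concern.** The primary objective (SAP 2.2.1) is the safety of ARO-HBV. Safety of ARO-HBV together with JNJ-6379 is a separate exploratory objective restricted to Cohort 12 (SAP 2.2.3). A pooled column labelled ARO-HBV that contains Cohort 12 merges the two questions.

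The pooled column has the largest denominator in the CHB tables, so readers will tend to quote it. In the all-causality event and laboratory summaries nothing filters events by drug. JNJ-6379 has its own profile: protocol 4.4 reports more headache than on placebo in healthy subjects, and protocol 4.7.2 names lipase, amylase and cholesterol as laboratory values of interest. If such events occur in Cohort 12, they raise the figure shown for ARO-HBV.

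**Working it through.** **1. Is Cohort 12 in the column?** The SAP does not say, so the evidence has to be set side by side.

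- Column list (SAP 3): Cohort 12 is listed with the other CHB cohorts and none is excluded from the combined column.
- Overall rule (SAP 3): summaries show cohorts and all subjects. *Combined ARO-HBV* is the only listed CHB column that could serve as the overall one.
- Recipients (SAP 2.5): all 13 CHB cohorts are described as receiving ARO-HBV, alone or with JNJ-6379.
- Sort key (SAP 10.1): only Cohort 12 takes JNJ-6379. If Cohort 12 were outside the combined group, that group would hold no JNJ-6379-related events to sort by.

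All four point to inclusion and nothing contradicts it. It remains an inference.

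**2. The plan's own totals** (cohort sizes from SAP 2.4). Six cohorts (1b to 5b) have 4 to 8 patients. Six cohorts (6 to 11) have at most 4, taken as 4 because no minimum is given. Cohort 12 has 12.

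- Minimum: 6×4 + 6×4 + 12 = 60
- Maximum: 6×8 + 6×4 + 12 = 84

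Both match SAP 2.4 and the protocol synopsis. Protocol 7.1 prints a minimum of 50, which these sizes do not give.

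**3. Share of the column.** 12/60 = 20.0% and 12/84 = 14.3%. Without Cohort 12 the denominator is 48 to 72.

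**4. Effect on a pooled rate.** With rate p in Cohorts 1b to 11 and q in Cohort 12:

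pooled = ((N − 12)p + 12q)/N, so the shift is (12/N)(q − p).

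| Assumed p | Assumed q | Pooled, N = 60 | Pooled, N = 84 |
|---|---|---|---|
| 10% | 30% | 14.0% | 12.9% |
| 20% | 50% | 26.0% | 24.3% |
| 10% | 10% | 10.0% | 10.0% |

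The p and q values are assumptions. An event in 3 of 12 Cohort 12 patients and nowhere else would read 3/60 = 5.0% or 3/84 = 3.6%.

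For a scale taken from the documents, protocol 4.4 gives headache in 27.6% on JNJ-6379 against 12.0% on placebo in healthy subjects, an excess of 15.6 points. If the same excess applied in Cohort 12 (an assumption), the shift would be 0.200 × 15.6 = 3.1 points or 0.143 × 15.6 = 2.2 points.

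**The case against.** Several arguments on the other side have force.

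- **Membership is inferred.** The sort-key bullet repeats the wording of the ARO-HBV bullet and may simply have been carried over. The matching table in SAP Section 19 (14.3.3.6.2) names no combined group. A reader might conclude that the SAP states outright that Cohort 12 is pooled; it does not. What stands is that the column is undefined and that the context favours inclusion.
- **The primary objective concerns related events, and the SAP separates relatedness by drug.** ARO-HBV-related events and serious events have their own tables, the overall summary is repeated for ARO-HBV- or placebo-related events, and JNJ-6379-related events have Cohort 12 tables. A reader might infer that JNJ-6379 events would be attributed to ARO-HBV throughout. That goes too far. The exposed items are the all-causality and laboratory summaries and the one row counting either drug. The ARO-HBV-related tables would still include 12 patients taking both drugs.
- **The pooled column is not the designated estimate.** SAP Section 10 summarizes each cohort separately. SAP 10.3.2 also describes laboratory summaries by cohort, so a combined laboratory column would come only from the Section 3 rule. Cohorts 1b to 11 already span six dose levels and three schedules, so removing Cohort 12 does not leave a single regimen.
- **Virology.** A reader might expect the mean 2.70 log10 fall in HBV DNA on JNJ-6379 250 mg (protocol 4.4) to be blended into ARO-HBV results. The documents do not support that size. SAP Section 11 specifies analyses by cohort, and its analysis of all CHB patients is optional. Protocol 4.4 reports no notable HBsAg change on JNJ-6379. The 2.70 came from treatment-naïve patients (protocol 4.8), whereas everyone here takes a nucleos(t)ide analogue.
- **The clean figure is recoverable.** Counts can be obtained by subtracting Cohort 12's column, provided the reader knows it was included. Medians and ranges cannot.
- **The shift is small against sampling error.** At a 10% rate the approximate 95% half-width is 1.96 × √(0.1 × 0.9/N), or 7.6 points at N = 60 and 6.4 at N = 84. The study is descriptive (SAP 2.4).

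**Conclusion.** The concern holds in limited form. The combined CHB column is undefined, and its most natural reading includes Cohort 12 at 14% to 20% of the denominator. Read that way, the all-causality adverse event, serious adverse event and laboratory summaries, and the overall-summary row for either drug, mix JNJ-6379 effects into an ARO-HBV label. The illustrative shifts above are a few percentage points and depend entirely on assumed rates; if Cohort 12's rates equal those elsewhere, there is no distortion. The conclusion rests on the inferred membership and on the planned cohort sizes. The virology consequence is minor. This is a cheap improvement to the pooled presentation. It does not invalidate the safety analysis, since every cohort is also shown separately.

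**What to change.** - In SAP Section 3, define *Combined ARO-HBV (Cohorts 1b to 11, excluding Cohort 12)*, n = 48 to 72. Use it in the CHB safety tables and in any virology table that shows a combined column.
- Keep Cohort 12 as its own column.
- If an all-CHB total (n = 60 to 84) is wanted, show it as a separate column whose label says that it includes the JNJ-6379 cohort.
- In SAP 10.1, sort the JNJ-6379-related table by incidence in Cohort 12.

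The cost is SAP wording, one redefined or extra column in tables that are already wide, and a pooled group smaller by 12. No data collection or trial conduct changes. The protocol already foresees analyses with and without Cohort 12, so this turns an option into a specification.

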- To determine the incidence and frequency of adverse events possibly or probably related to treatment as a measure of the safety and tolerability of ARO-HBV in combination with JNJ-6379 in patients chronically infected with hepatitis B virus (CHB) (Cohort 12 only).

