- Study Drug (ARO-HBV or placebo) Related SAEs by SOC and PT
- Study Drug (JNJ-6379) Related SAEs by SOC and PT (Cohort 12 only)
- TEAEs Leading to Study Drug or Study Withdrawn
- TEAEs occurring at the treatment injection site by SOC (General disorders and administration site conditions) and PT linked to High Level Term, "Injection Site Reaction"
- TEAEs fitting the definition of LISR by SOC and PT

A by-subject AE data listing, including verbatim term, MedDRA SOC and PT, severity, outcome and relationship to study treatment, will be provided. Separate listings will be generated for SAEs. AEs that started during the follow-up period will be flagged. Cohort 12 data will be listed separately.

Local Injection Site Reactions (LISR)

Local Injection Site Reactions will be reviewed based on description of symptoms, level of severity (mild, moderate or severe) and outcome of the reactions as well as other relevant data elements such as de/re-challenge, medical history, and possible confounding variables. Based on the review, the reactions will be specifically categorized and collated for the analysis.

The results will be summarised by cohort across all dose levels and percentages for the reported LISR by using the MedDRA coding system by System Organ Class (SOC), General disorders and administration site conditions and Preferred Terms that are associated with local injection site reactions.

The following MedDRA Preferred Terms determined by the Sponsor's pharmacovigilance personnel represent the local injection site reaction:

Injection site discomfort	Injection site abscess
Injection site discoloration	Injection site abscess sterile
Injection site erythema	Injection site atrophy
Injection site irritation	Injection site calcification
Injection site inflammation	Injection site cellulitis
Injection site induration	Injection site dermatitis
Injection site pain	Injection site erosion
Injection site oedema	Injection site fibrosis
Injection site pruritus	Injection site indentation
Injection site rash	Injection site necrosis
Injection site urticaria	Injection site nodule
Injection site reaction	Injection site ulcer
Injection site swelling	

Those summaries will only include events that start on the day of injection and persist for at least 2 days (48 hours) post injection (i.e., event onset date on the day of injection and

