14.2.4.11	Summary of Cellular Immunology Parameters [CHB cohorts in New Zealand only]	PD	
14.2.5.1	Summary of Cytokine Parameters [Panel A for NHV cohorts, Panel B for CHB cohorts]	PD	X
14.2.6.1	Summary of Complement Parameters [NHV cohorts]	PD	X
14.3.1.1	Summary of Concomitant Medications and Non-Drug Therapies	Safety	X
14.3.3.1	Overall Summary of Treatment Emergent Adverse Events	Safety	X
14.3.3.2	Summary of Treatment Emergent Adverse Events by System Organ Class and Preferred Term	Safety	X
14.3.3.3	Summary of Treatment Emergent Adverse Events in Descending Order of Frequency by Preferred Term	Safety	X
14.3.3.4	Overall Summary of Related Treatment Emergent Adverse Events	Safety	X
14.3.3.5.1	Summary of Related Treatment Emergent Adverse Events by System Organ Class and Preferred Term	Safety	X
14.3.3.5.2	Summary of JNJ-6379 Related Treatment Emergent Adverse Events by System Organ Class and Preferred Term (Cohort 12) [CHB Cohort 12 only]	Safety	X
14.3.3.6.1	Summary of Related Treatment Emergent Adverse Events in Descending Order of Frequency by Preferred Term	Safety	X
14.3.3.6.2	Summary of JNJ-6379 Related Treatment Emergent Adverse Events in Descending Order of Frequency by Preferred Term (Cohort 12) [CHB Cohort 12 only]	Safety	X
14.3.3.7	Summary of Treatment Emergent Adverse Events by System Organ Class and Preferred Term and by Severity	Safety	X
14.3.3.8	Summary of Treatment Emergent Adverse Events by System Organ Class and Preferred Term and by Relationship to Study Drug	Safety	X
14.3.3.9	Summary of Serious Treatment Emergent Adverse Events by System Organ Class and Preferred Term	Safety	X
14.3.3.10.1	Summary of Serious Study Drug Related Treatment Emergent Adverse Events by System Organ Class and Preferred Term	Safety	X

No.	Title	Analysis Population	Day 113: Interim Analysis
14.3.3.10.2	Summary of Serious JNJ-6379 Related Treatment Emergent Adverse Events by System Organ Class and Preferred Term (Cohort 12) [CHB Cohort 12 only]	Safety	X
14.3.3.11	Summary of Treatment Emergent Adverse Events Leading to Study Drug or Study Withdrawn	Safety	X
14.3.3.12	Summary of Treatment Emergent Adverse Events Occurring at the Treatment Injection Site	Safety	X
14.3.3.13	Summary of Treatment Emergent Adverse Events Fitting the Definition of Local Injection Site Reactions (LISR) (See LISR definition in Section 10.1)	Safety	X

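### For Cohort 12 the SAP uses two meanings of a related adverse event across its tables, and no by-term table shows events related to either study drug

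*SAP*

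**What the plan says.** Protocol 5.3 sets an exploratory objective for Cohort 12, to establish how often there are "adverse events possibly or probably related to treatment as a measure of the safety and tolerability of ARO-HBV in combination with JNJ-6379". The Data Analysis part of the protocol synopsis and protocol 11.4 plan summaries of related AEs and related SAEs by system organ class (SOC) and preferred term (PT).

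SAP 10.1 defines relatedness in the overall AE table as "TEAE related to study treatment (related to ARO-HBV or JNJ-6379 [Cohort 12 only]: possibly/probably". It then states: "The table will also be repeated for related (ARO-HBV or placebo) TEAEs". The list that follows includes:

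- one by-relationship table: "TEAEs by Relationship to Study Drug (ARO-HBV";
- a by-term related table for the siRNA: "Study Drug (ARO-HBV or placebo) Related TEAEs by SOC and PT";
- Cohort 12 tables for the other drug, among them "Study Drug (JNJ-6379) Related TEAEs by SOC and PT (Cohort 12 only" and "Study Drug (JNJ-6379) Related SAEs by SOC and PT (Cohort 12 only".

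In SAP 19, Table 14.3.3.8 is titled "Summary of Treatment Emergent Adverse Events by System Organ Class and Preferred Term and by Relationship to Study Drug". Neither that title nor the title of 14.3.3.4 says which drug is meant. SAP 4 (Safety Population) takes study treatment to be ARO-HBV or JNJ-6379, and SAP 8 lists JNJ-6379 among the study drugs.

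**The concern.** The same 12 patients can show different related totals in 14.3.3.1 and 14.3.3.4. A reader who applies the SAP's own meaning of study drug to the title of 14.3.3.8 could take an event attributed only to JNJ-6379 as unrelated to anything the patient received.

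Such events are foreseeable. Protocol 4.4 and 4.7.2 name lipase and amylase elevations as laboratory abnormalities of interest for JNJ-6379, and the pooled healthy-subject data show them in 5 and 6 subjects on JNJ-6379 against none on placebo.

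At stake is the by-term safety picture for the combination. The natural reading of treatment in the Cohort 12 objective is either drug, yet no planned SOC/PT table uses that definition.

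**Working it through.** The plan states no figure on this point. The check traces one type of event through the tables, then asks whether the missing count can be rebuilt.

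**Inputs.** Definitions come from SAP 10.1, table numbers and titles from SAP 19, and the cohort size of 12 from SAP 2.4. The documents give no event counts, so the patient counts in step 2 are assumed.

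**Step 1: where a Cohort 12 event attributed only to JNJ-6379 appears.**

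| Table | Relatedness used | JNJ-6379-only event |
|---|---|---|
| 14.3.3.1 overall | either drug | related |
| 14.3.3.4 repeat for related events | ARO-HBV or placebo | absent |
| 14.3.3.5.1, 14.3.3.6.1 by term | ARO-HBV or placebo | absent |
| 14.3.3.5.2, 14.3.3.6.2 by term | JNJ-6379 | related |
| 14.3.3.8 by relationship | ARO-HBV | not related |
| 14.3.3.10.1 serious | ARO-HBV or placebo | absent |
| 14.3.3.10.2 serious | JNJ-6379 | related, if serious |

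No row combines either-drug relatedness with SOC and PT.

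**Step 2: can the either-drug count for one PT be recovered?** Let a be the patients with that PT related to ARO-HBV, b those with it related to JNJ-6379, and u those with it related to at least one. A patient counted under both drugs appears in both tables, so

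max(a, b) ≤ u ≤ min(12, a + b).

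| a, b (assumed) | range of u | % of 12 |
|---|---|---|
| 1, 1 | 1 to 2 | 8.3 to 16.7 |
| 2, 2 | 2 to 4 | 16.7 to 33.3 |
| 3, 3 | 3 to 6 | 25.0 to 50.0 |
| 4, 4 | 4 to 8 | 33.3 to 66.7 |

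The all-cause table by SOC and PT (14.3.3.2) gives a further cap. If c patients have the PT from any cause, then u ≤ min(12, a + b, c). With a = b = 3 and an assumed c = 4, the range shrinks to 3 to 4 of 12 (25.0% to 33.3%).

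When one count is zero, u is exact. With a = 0 and b = 3, u = 3 of 12 (25.0%), while an ARO-HBV relationship table shows 0 of 12 related.

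**Step 3: patient level.** Table 14.3.3.1 reports directly the patients with at least one event related to either drug. The serious and grade 3 or higher related rows follow in the same sentence of SAP 10.1, and I read the same definition as carrying over to them. No bounds are needed for these three figures.

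**The case against.** The strongest reply is that the plan already answers the objective. It asks for incidence and frequency, and 14.3.3.1 gives either-drug incidence overall, for serious events and for grade 3 or higher. Three Cohort 12 tables show JNJ-6379-related events as related. In a table of relationship to ARO-HBV, an event caused only by JNJ-6379 is correctly not related. The objective is exploratory, SAP 10 calls the safety analysis primarily descriptive, and Cohort 12 has its own AE listing with relationship, so with 12 patients the by-term count can be made by hand. Redefining related throughout the multi-cohort tables would also do harm: SAP 3 does not exclude Cohort 12 from the Combined ARO-HBV group, so JNJ-6379-only events could enter pooled rates meant for ARO-HBV.

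Most of this stands. A reader might infer that JNJ-6379-related events are generally reported as unrelated, or that the related rate in Cohort 12 cannot be determined at all. The documents support neither: the dedicated tables refute the first and 14.3.3.1 refutes the second. The warning about the combined column stands too and shapes the fix.

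Two parts do not stand. The ARO-HBV qualifier is in the SAP text but not in the listed title of 14.3.3.8, and 14.3.3.4 repeats the overall table under a different definition that its title does not disclose. And by-term reporting is not an optional extra, since the protocol itself plans related AEs and SAEs by SOC and PT.

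**Conclusion.** The point holds as a narrow inconsistency. Relatedness in Cohort 12 means either drug in 14.3.3.1, ARO-HBV or placebo in 14.3.3.4, and ARO-HBV in 14.3.3.8; the titles of the last two hide the change; and no SOC/PT table gives either-drug relatedness.

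The gap is per term. Its width is the difference between max(a, b) and the smallest of 12, a + b and the all-cause count: up to 3 patients (25 percentage points) in the assumed 3-and-3 case, and nothing where only one drug is implicated. A reader might be tempted to apply these ranges to the overall patient-level related rate; that is wrong, because 14.3.3.1 reports that rate exactly.

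The conclusion assumes 12 treated patients in Cohort 12, separate causality attributions to each drug (which the planned tables require), and treatment in the objective meaning either drug. Practical impact is modest, since the listing allows a hand count, but the report would carry conflicting related totals for one cohort without explanation.

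**What to change.** In SAP 10.1 and 19:

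- Produce 14.3.3.4 for Cohort 12 with the same either-drug definition as 14.3.3.1, most simply as a separate Cohort 12 version.
- Add Cohort 12 tables, by SOC and PT, of TEAEs and of SAEs related to ARO-HBV and/or JNJ-6379.
- Add a Cohort 12 by-relationship table covering JNJ-6379 or either drug.
- Keep the existing ARO-HBV and JNJ-6379 tables as breakdowns by attribution, and keep JNJ-6379-only events out of the Combined ARO-HBV column of the ARO-HBV-related tables.
- Name the drug in the title of every table of related events.

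The cost is a few extra outputs and one flag derived from causality data the planned tables already need. No new data are collected. The related rate shown for Cohort 12 in 14.3.3.4 will rise if any patient's related events are attributed only to JNJ-6379; a footnote should explain why.
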